24 HOUR RANDOMISATION

Web https://lictr.leeds.ac.uk/webrand/ or [contact]

Please ensure that informed consent has been taken and eligibility is confirmed prior to phoning the randomisation line / accessing the web randomisation

NB: Access codes will be required.

Immediately after randomisation, please send the Consent Form and Contact Form to CTRU via fax or secure file transfer

[contact]

9.4.3 TREATMENT ALLOCATION

Participants will be randomised on a 1:1 basis to receive either laparoscopic or open surgery and will be allocated a unique trial number. Randomisation will be based on a minimisation algorithm with random component ensuring that treatment groups will be balanced for the following minimisation factors:

- Intended Consultant Surgeon in charge
- Patient age
 - o **18-<50**
 - o **50-59**
 - o **60-69**
 - o **70-79**
 - o ≥80
- Body Mass Index (kg/m²)
 - <25 kg/m²
 - o 25-<30 kg/m²
 - o ≥30 kg/m²
- ASA status
 - o I or II A normal healthy patient or A patient with mild systemic disease.
 - III A patient with severe systemic disease.
 - IV Or V A patient with severe systemic disease that is a constant threat to life or A moribund patient who is not expected to survive without the operation.
- Nature of underlying colorectal pathology
 - o Benign
 - o Malignant
 - o Unsure
- Nature of intended surgical procedure
 - Segmental colectomy, Right hemicolectomy, Left Hemicolectomy or Sigmoid Colectomy
 - Hartmann's procedure
 - o Subtotal colectomy
 - o Other

10 INTERVENTION DETAILS

10.1 SCHEDULE OF CLINICAL ASSESSMENTS/DATA COLLECTION POINTS

The timing of clinical assessments and data collections points are summarised in Table 1. All participants will be followed up until 12 months post-operation.

Table 1 Schedule of events

	Events	Pre-trial diagnostics	Baseline/ pre-op	Surgery	Hospital discharge	30 days post-op (QoL only)	6 weeks post- op ²	90 days post- op ³	6 months post-op (no clinic visit - data from medical notes)	9 months post-op (QoL only)	12 months post-op (no clinic visit - data from medical notes)
nts/	Radiological/endoscopic diagnosis ⁴	V									
	Clinical examination		V				V	V			
Clinical assessments/ investigations	Trial consent		V								
l asse estige	Operative details			V							
Clinica	Complications			V			V	V	V		v
0	Re-operations/re- admissions						V	V	V		V
	Eligibility CRF		٧								
Data collection time points	Baseline CRF		v								
	Operative CRF			V							
	Discharge CRF				v						
Dai	Post-operative f/up CRF						V	V	V		v
s	GIQLI					V		V	V	v	v
Participant completed questionnaires	SF-12 [®]		V			V		V	V	v	v
	EQ-5D-5L™		V			V		V	V	v	v
d onb	Health Resource Use		V			V		V	V	v	v

 ² It is permissible for this visit to be conducted via telephone if it is not possible to see the participant in clinic
 ³ It is permissible for this visit to be conducted via telephone if it is not possible to see the participant in clinic
 ⁴ As part of standard clinical practice

10.2 PRE-OPERATIVE INVESTIGATIONS AND PREPARATION

Pre-operative investigation and treatment will be as per institutional protocol and must include radiological imaging i.e. CT or MRI scan and/or endoscopy.

10.3 SURGERY

Conventional laparoscopic and open surgery should be undertaken in keeping with standard practice and overseen/performed by the randomising surgeon, the only difference is the operative approach. The specifics of each operation will be at the discretion of the operating surgeon, as will the decision to convert to an open operation.

Laparoscopic surgery includes the use of multi-port or single-port incisions to establish pneumoperitoneum to enable resection. Conversion to an open operation will be defined as the use of a midline laparotomy wound for any part of the colorectal dissection. The use of a limited laparotomy wound to facilitate specimen extraction is permissible.

10.4 POST-OPERATIVE CARE

Post-operative care will be as per institutional protocol. Participants will be followed up for 12 months post-operatively for trial purposes. Clinical, patient-reported outcome and health economic data will be collected at baseline, 30 days (patient-reported), 6 weeks, 90 days, 6 months, 9 months (patient-reported) and 12 months post-operatively.

10.5 PARTICIPANT WITHDRAWAL

In line with usual clinical care, cessation or alteration of treatment at any time will be at the discretion of the attending clinician or the participant themselves.

In the event that a participant withdraws prior to randomisation, no further data is required to be submitted. In the event that a participant withdraws after randomisation (prior to, or after their operation) participants will still attend follow-up visits unless unwilling to do so and safety data and follow-up data will continue to be collected.

If a participant explicitly states that they do not wish to contribute further data to the trial or to complete any further participant questionnaires, the CTRU must be informed via the Withdrawal eCRF on the LaCeS2 database.

The PI or delegate must make every effort to ensure that the specific wishes of any participant who wishes to withdraw consent for further involvement in the trial are defined and documented using the **Withdrawal eCRF within 7 days** of the withdrawal request in order

that the correct processes are followed by the CTRU and research site following the withdrawal of consent.

11 DATA COLLECTION

Participating research sites will be expected to maintain a file of essential trial documentation (ISF), which will be provided by the CTRU, and keep copies of all completed CRFs for the trial. Paper CRFs, eCRFs and participant-completed questionnaires will contain the participant's unique trial number, date of birth, and initials. Clinical data will be collected at baseline, operation, hospital discharge and at 6 weeks, 90 days, 6 months and 12 months post-operation; participant-completed data will be collected at baseline and at 30 days, 90 days, 6 months, 9 months and 12 months post-operation.

11.1 SUBMISSION OF TRIAL DATA

Informed Consent Documents, Contact Details forms and Serious Complication data (SCs/USCs) requiring expedited reporting (see section 12.3.1) will be collected via paper case report forms (CRFs). Baseline participant-completed questionnaires will be collected on paper, and follow-up participant-completed questionnaires will be collected either on paper or electronically via patient-reported outcome software, dependent on participant choice. All other data collection will be via Remote Data Entry (RDE) on electronic case report forms (eCRFs) managed by the CTRU at the University of Leeds. Access to the live LaCeS2 database will be provided by the CTRU following sites being authorised to open to recruitment. An SSOP will offer guidance on RDE and completing the eCRFs. Missing and discrepant data will be flagged and additional data validations raised as appropriate by the CTRU data management team.

Data collected on paper CRFs (Consent, Contact details, SCs and USCs) will be sent to the CTRU, usually via standard post but in some cases by fax, email or secure electronic transfer. If Informed Consent Documents are posted to CTRU, they must be sent in a separate envelope to participant questionnaires.

Data must only be completed by personnel authorised to do so by the PI, as recorded on the trial-specific Authorised Personnel Log.

11.2 PRE-TREATMENT DATA COLLECTION

Participants must be screened, assessed for eligibility and have provided written informed consent before they can then be randomised (Section 9.4)

Data will be entered onto pre-operative eCRFs on the LaCeS2 database (Eligibility Checklist, Baseline and Randomisation Forms) and will include (but will not be limited to):

- Personal details and demographics including height, weight and sex
- Date of diagnosis
- Diagnosis at baseline
- Nature of intended surgical procedure
- Confirmation of eligibility
- Confirmation of written informed consent
- Minimisation factors (see section 9.4.3)
- Concomitant diseases/co-morbidities
- Details of previous abdominal operations

Following written informed consent, and wherever possible prior to randomisation (where this is not possible this must be prior to the participant being made aware of their randomised treatment), participants will also be asked to complete the baseline participant-completed questionnaires:

- SF-12[®]
- EQ-5D-5L[™]
- Health Resource Use

11.3 OPERATIVE DATA COLLECTION

Operative data will be entered into the Operative eCRF on the LaCeS2 database and will collate data relating to the surgical operation including (but not limited to):

- Consultant surgeon in charge
- Grade of operating surgeon
- Operative approach
- Type of operation performed
- Duration of operation
- Estimated blood loss
- Whether conversion to open surgery occurred, details and reason (laparoscopic arm only)
- Any intra-operative complications
- Staff present
- Intraoperative analgesic regime
- Operative findings

11.4 FOLLOW-UP DATA COLLECTION

11.4.1 DISCHARGE DETAILS

Hospital discharge details will be entered onto the Discharge eCRF in the LaCeS2 database at the point at which participants are discharged from hospital. Data collected will include (but will not be limited to):

- Date of discharge
- Date of restoration of gastrointestinal function, if applicable

11.4.2 REOPERATIONS

If the participant undergoes any further abdominal operations within 6 weeks of their index emergency operation, please complete the Re-operative eCRF.

11.4.3 DATA COLLECTION FOR CLINICAL ASSESSMENTS

Post-operative care will be as per institutional protocol. However, a clinical assessment must be carried out for all participants at 6 weeks and 90 days post-operation. The 6-month and 12-month post-operative assessment can be completed from participants' medical notes; participants do not need to be seen in clinic for trial purposes at these time points. Data collected during follow-up will include (but will not be limited to):

- Participant status (dead/alive)
- Complications
- Readmissions
- Reoperations (see section 11.4.2 for additional details)
- Details of further abdominal surgeries

At the post-operative reviews participants will be asked to complete the participant questionnaire booklets; for details of questionnaires completed at each post-operative review refer to section 11.5.

11.5 PARTICIPANT-COMPLETED QUESTIONNAIRES

Participants will complete a number of health related quality of life questionnaires at various time points throughout their participation in the trial (see Table 1). The following questionnaires will be included in each questionnaire pack, unless otherwise specified:

- Gastrointestinal Quality of Life Index (GIQLI): Disease-specific HrQoL will be measured using the GIQLI. The GIQLI is composed of 36 items with 5 answer categories for each item (0-4). The GIQLI has been validated for use in patients with all gastrointestinal disease including colorectal disease requiring operative intervention [13, 14]. The GIQLI questionnaire will be included in the follow-up questionnaire packs only (i.e. at 30 days, 90 days, 6 months, 9 months and 12 months post-operation).
- **EQ-5D-5L**[™]: a well-validated questionnaire used to assess generic Quality of Life [15], it provides a simple descriptive profile and a single index value for health status.
- SF-12[®]: Generic HrQoL will be measured using the SF-12[®] questionnaire. SF-12[®] is a 12-item subset of the SF-36v2[®] that measures the same eight domains of health. The SF-12[®] is a well validated HrQoL tool for use in the acute setting with a short recall period of 1 week [16-18].
- Health Resource Use: is composed of questions related to contact with primary, community and social care services.

All participants will complete the health related quality of life questionnaire packs at baseline⁵, 30 days, 90 days, 6 months, 9 months and 12 months post-operatively.

The baseline quality of life questionnaire pack will be completed by participants on paper at the participating local research site, either in A&E, surgical assessment units, surgical wards or in clinic. Participants will be asked to seal their completed baseline questionnaire pack in a pre-supplied envelope prior to giving it to the local research staff, who will then send the sealed envelope to the CTRU for entry into the trial database.

All subsequent questionnaire packs (30 days, 90 days, 6 months, 9 months and 12 months post-operation) will be administered directly to participants by the CTRU trial team. Participants will have the option to complete the post-operative questionnaires in paper format or electronically, depending on their personal preference. Participants who have chosen to complete their questionnaires in paper format will receive the questionnaire packs from the CTRU trial team by post and will be asked to return the completed questionnaires to the CTRU using a pre-supplied stamped, addressed envelope. For participants who choose to complete the questionnaires electronically, SMS and/or emails will be sent to the participants from the

⁵ Baseline questionnaires must be completed after consent and, wherever possible, prior to randomisation (where this is not possible, they must be completed prior to the participant being made aware of their randomised treatment).

CTRU with the link to the questionnaire and to prompt completion. A thank you will be sent to participants by the CTRU upon receipt of a completed questionnaire. Should a completed questionnaire not be received at the CTRU by the required time-point, the CTRU will send one reminder to the participant either by post, SMS or email (depending on the participant's questionnaire-completion preferences).

11.6 **DEATH**

All deaths must be recorded on the Notification of Death eCRF. Data collected will include (but will not be limited to):

- Date of death
- Cause of death

Deaths occurring in the study population from the date of consent to 12 months post-operation must be reported on the **Notification of Death eCRF** on the LaCeS2 database **within 7 days** of site becoming aware of the event.

11.7 DEFINITION OF END OF TRIAL

The end of the trial is defined as the date of the last participant's last data item.

11.8 PROTOCOL DEVIATIONS

The CTRU undertake to adopt all reasonable measures to record data in accordance with the protocol. Under practical working conditions, however, some minor variations may occur due to circumstances beyond the control the CTRU. All such deviations will be documented on the study records, together with the reason for their occurrence; where appropriate, deviations will be detailed in the published report.

12 SAFETY REPORTING

For the purpose of this surgical trial, the safety reporting terms adverse events and serious adverse events have been translated into complications. The current evidence base suggests 30-day morbidity rates of 33-71% in patients undergoing an emergency laparotomy. Consequently, the proportion of patients experiencing complications and serious complications is anticipated to be high, reflecting current clinical practice.

All reported 30-day post-operative complications for the first 5 recruited patients at each site will be independently reviewed by the CTRU to ensure accurate reporting. Anticipated complications are outlined in Appendix 2, although this is not an exhaustive list.

12.1 GENERAL DEFINITIONS

A **complication** is defined as an untoward medical event in a participant, which has a causal relationship to the trial. The trial includes the surgical intervention and any trial specific interventions e.g. the consent process and completion of questionnaires.

An untoward medical event can include:

- any unintentional, unfavourable clinical sign or symptom
- any new illness or disease or the deterioration of existing condition
- any clinically relevant deterioration in any clinical tests

A serious complication is defined as a complication which:

- results in death
- is life-threatening⁶
- requires in-patient hospitalisation or prolongation of existing hospitalisation
- results in persistent or significant disability or incapacity
- consists of a congenital anomaly or birth defect, or
- is otherwise considered medically significant by the investigator

Serious complications occurring within 30 days of the participant's operation will be subject to expedited reporting requirements (see section 12.3 for further details).

An **Unexpected Serious Complication (USC)** is a **serious** complication which is **related** and **unexpected** and will require expedited reporting (see section 12.3) to enable reporting to the main Research Ethics Committee (REC) and Sponsor.

The Health Research Authority (HRA) defines the terms related and unexpected as:

• **Related**: that is, it resulted from administration of any research procedures. All complications by definition are related to the trial procedures. (Untoward medical events which are unrelated to the trial procedures are not being collected in this trial).

⁶ Life-threatening refers to an event in which the participant was at risk of death at the time of the event, NOT an event which hypothetically may have caused death had it been more severe.

• **Unexpected**: that is, the type of event that in the opinion of the investigator is not considered expected. Examples of expected complications are provided in Appendix 2; note this is not an exhaustive list.

Medical and scientific judgement must be exercised in deciding whether an event is serious (see section 12.4 for Responsibilities). These characteristics/ consequences must be considered at the time of the event and do not refer to an event which hypothetically may have caused one of the above.

12.2 GRADING OF COMPLICATIONS

Intra-operative complications will be graded using the ClassIntra[®] classification of intraoperative adverse events [19]. Similar to the Clavien-Dindo classification for post-operative complications, ClassIntra[®] classifies intra-operative complications into 5 grades of increasing severity (see Appendix 4). Post-operative complications will be graded according to the Clavien-Dindo classification [20, 21]. This is an acceptable and validated method of documenting surgical complications. The system is divided into 7 grades (I, II, IIIa, IIIb, IVa, IVb and V), reflecting the varying severity of complications (see Appendix 3). The Clavien-Dindo classification grades the severity of complications by assigning a grade to the most severe complication. The Comprehensive Complication Index is a continuous measure which calculates the severity and grade of all experienced post-operative complications [22].

12.3 REPORTING OF COMPLICATIONS

Information on all complications which occur from the date of consent until the end of followup (12 months post-surgery) will be collected in this trial whether volunteered by the participant, discovered by investigator questioning or detected through physical examination or other investigation.

12.3.1 SERIOUS COMPLICATIONS (SCs) AND UNEXPECTED SERIOUS COMPLICATIONS (USCs) OCCURRING WITHIN 30 DAYS OF THE OPERATION – EXPEDITED REPORTING

All serious complications (SCs) and unexpected serious complications (USCs) (see section 12.1) which occur within 30 days of the operation are subject to expedited reporting requirements and must therefore be notified to the CTRU within 24 hours of the clinical research staff becoming aware of the event. Notifications must be sent to the CTRU by fax or email using the SC/USC CRF. Once all resulting queries have been resolved, the CTRU will request that the original form is posted to the CTRU and a copy retained at site.

24 hour fax for reporting SCs and USCs: [name]

Email: [contact]

For each SC and USC, the following data will be collected:

- Start and end dates of event, if resolved
- Full details of complication in medical terms with a diagnosis
- Action/Intervention
- Outcome
- An identifiable and authorised reporting source (i.e. the signature of the investigator or other medic authorised by the investigator at the reporting research site)

Any follow-up information on SCs and USCs must be faxed or emailed to the CTRU as soon as it is available. Events will be followed up until the event has resolved or a final outcome has been reached. All SCs and USCs will be reviewed by the Chief Investigator or delegate. USCs are subject to expedited reporting to the Sponsor and the main REC by the CTRU on behalf of the Chief Investigator in accordance with current NRES guidance, CTRU Standard Operating Procedures (SOPs), and Sponsor requirements.

SCs and USCs with an onset date greater than 30 days post-operation are not subject to expedited reporting, but must be reported with all other types of complication (i.e. non-serious expected and unexpected complications) on the standard post-operative follow-up eCRFs.

12.3.2 ALL OTHER COMPLICATIONS – NON-EXPEDITED REPORTING

Information about the incidence and severity of all other complications (this includes all nonserious expected and unexpected complications) which occur from the date of consent until 12 months post-operation will be collected for all participants on the Operative eCRF or on the Post-operative Follow-Up Assessment eCRFs, as appropriate. This also applies to any SCs or USCs with an onset date greater than 30 days post-operation. These events will **not** be subject to expedited reporting requirements.

12.3.3 UNTOWARD MEDICAL EVENTS UNRELATED TO THE STUDY

It is anticipated that there will be minimal additional risks associated with the interventions in this study. Participants treated may have co-morbidities and in recognition of this, untoward medical events will only be reported if they are classified as related to study procedures (including the surgical intervention and related procedures or study-specific procedures such as consent and questionnaire completion).

12.4 RESPONSIBILITIES FOR SAFETY REPORTING

Principal Investigator (PI) (i.e. lead study clinician at each recruiting research site or appropriate clinical individual identified in the Authorised Personnel Log)

- Checking for complications during admission and follow-up, including judgment in assigning:
 - Causality, i.e. whether an untoward medical event is related (i.e. a complication which therefore needs to be reported) or unrelated (i.e. not a complication and therefore does not need to be reported)
 - Seriousness
 - Expectedness
- To ensure that all SCs and USCs which occur within 30 days post-operation are recorded and initially reported to the CTRU within 24 hours of the research team becoming aware and to provide further follow-up information as soon as it is available.
- To report all other complications (SCs and USCs occurring beyond 30 days postoperation and non-serious complications) to the CTRU in line with the protocol during the trial follow-up period.
- To report USCs to local committees in line with local arrangements

Chief Investigator (CI) (or nominated individual in CI's absence)

- Assign relatedness and expected nature of reported complications/untoward medical events where it has not been possible to obtain local assessment.
- Undertake review of SCs and USCs (see section 12.3.1).
 - In the event of disagreement between local assessment and the CI, local assessment may be upgraded or downgraded by the CI prior to reporting to the REC.

Clinical Trials Research Unit (CTRU)

 Expedited reporting of USCs occurring within 30 days post-operation to the REC and Sponsor within required timelines.

- Preparing annual safety reports to the REC and periodic safety reports to the Trial Steering Committee (TSC) and Data Monitoring and Ethics Committee (DMEC) as appropriate
- Notifying Investigators of SCs and USCs which compromise participant safety.

Trial Steering Committee (TSC)

In accordance with the TSC Terms of Reference and CTRU policies, periodically reviewing safety data and liaising with the DMEC regarding safety issues.

Data Monitoring and Ethics Committee (DMEC)

In accordance with the DMEC Terms of Reference and CTRU policies, periodic review of unblinded safety data to determine patterns and trends of events and to identify any safety issues which would not be apparent on an individual case basis.

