7 DESIGN

7.1 TRIAL DESIGN

LaCeS2 is a phase III prospective, multicentre, pragmatic, unblinded, two-arm individually randomised controlled superiority trial, investigating the clinical effectiveness and cost-effectiveness of laparoscopic colorectal emergency surgery compared to open surgery. The trial includes a 12-month internal pilot phase (Section 7.2) and embedded qualitative study (Section 22). Recruitment will be conducted within acute general surgery services.

A total of 512 adult, consenting patients requiring emergency colorectal surgery will be randomised over 3 years on a 1:1 basis between laparoscopic and open surgery using minimisation (incorporating a random element).

All participants will be followed up for a period of 12 months post-operatively, providing clinical and patient-reported outcomes. The trial will not be blinded to participants, medical or trial staff for pragmatic reasons, based on the results of the feasibility study.

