20.2 OVERSIGHT/TRIAL MONITORING GROUPS

Trial Management Group (TMG): the TMG, comprising the CI, CTRU team, other key external members of staff involved in the trial, and a patient representative will be assigned responsibility for the clinical set-up, on-going management, promotion of the trial, and for the interpretation of results. Specifically the TMG will be responsible for:

- Protocol completion
- CRF development
- Obtaining approval from the HRA, UK REC and supporting applications for Site Specific Assessments (SSAs)
- Completing cost estimates and project initiation
- Nominating members and facilitating the TSC and DMEC
- Reporting of complications
- Monitoring of screening, recruitment, treatment and follow-up procedures
- Auditing consent procedures, data collection, trial end-point validation and database development.

Trial Steering Committee (TSC): the TSC will have overall responsibility for the external oversight of the trial. The TSC will provide overall blinded monitoring of the trial, in particular trial progress, adherence to protocol, participant safety and consideration of new information. It will include an independent Chair, not less than two other independent members, and a consumer representative. The CI and other members of the TMG may attend the TSC meetings and present and report progress. The independent Committee will meet annually as a minimum and will consider recommendations made by the independent DMEC.

Data Monitoring and Ethics Committee (DMEC): the independent DMEC will review the safety of participants and ethics of the trial by reviewing interim data during recruitment and follow-up. The DMEC will be comprised of between 3 and 5 independent voting members, at least one of whom will be a statistician, and at least one of whom will be a clinician experienced in the relevant area; one DMEC member will assume the role of Chair. DMEC meetings will consist of an open session to discuss aggregate data with the wider trial team and, a closed session, where data (as agreed and specified in the DMEC Charter) will be presented by randomised group and discussed only with the Trial Statisticians. The Committee will meet annually as a minimum and make recommendation regarding continuation, specifically following the internal pilot phase to the TSC.

Public Patient Involvement (PPI): A PPI representative will sit on the Trial Management Group and there will also be a PPI representative on the Trial Steering Committee. The PPI

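### Section 12.4 lets the unblinded Chief Investigator take a site-reported event out of expedited ethics reporting by downgrading it, and leaves the effect on the primary outcome unsettled

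*Protocol*

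**What the plan says.** **Who reviews.** Section 12.3.1, on serious complications (SCs) and unexpected serious complications (USCs) within 30 days: "All SCs and USCs will be reviewed by the Chief Investigator or delegate". Section 12.4 adds that, on disagreement, "local assessment may be upgraded or downgraded by the CI prior to reporting to the REC". It does not say which attributes may be changed (seriousness, relatedness or expectedness), or that the site's view travels with the CI's.

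**Blinding.** Section 7.1: "The trial will not be blinded to participants, medical or trial staff for pragmatic reasons". No masked review of complications is described.

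**What goes to the REC by expedited report.** Section 12.4 gives the CTRU this task: "Expedited reporting of USCs occurring within 30 days post-operation to the REC and Sponsor within required timelines". Under section 12.1 a USC must be serious, related and unexpected.

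**What counts as a complication.** Section 12.1: a complication "is defined as an untoward medical event in a participant, which has a causal relationship to the trial". The same section says: "Untoward medical events which are unrelated to the trial procedures are not being collected in this trial".

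**What the primary outcome counts.** Section 13.1 counts patients with a post-operative complication of any grade within 30 days, out of all randomised.

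**What happens before CI review.** The site's report "must therefore be notified to the CTRU within 24 hours of the clinical research staff becoming aware of the event" (section 12.3.1).

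**End-point validation.** Section 20.2 lists this among the duties of the Trial Management Group (TMG), which includes the CI: "Auditing consent procedures, data collection, trial end-point validation and database development". Masking is not mentioned.

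**The concern.** Two things are at stake.

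The first is the safety route. The site has seen the patient and judged the event serious, related and unexpected. The CI, who knows the allocation, can lower one of those judgements, and the event then no longer qualifies for expedited reporting to the REC and Sponsor. No rule sends both opinions forward.

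The second is the primary outcome. In most trials a causality call is a safety attribute and leaves the efficacy count alone. Here causality is built into the definition of a complication, and complications are the primary outcome. A change of relatedness made for safety reporting therefore bears on whether the event meets the endpoint definition at all. In an unblinded superiority trial it should be settled in advance that reclassification by someone who knows the arm cannot alter the endpoint.

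**Working it through.** **Step 1. What each kind of downgrade would do**

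| Attribute lowered by the CI | Still a USC (12.1)? | Still a complication (12.1)? | Still meets the any-grade endpoint (13.1)? |
|---|---|---|---|
| Expectedness (unexpected to expected) | No | Yes | Yes |
| Seriousness (serious to non-serious) | No | Yes | Yes |
| Relatedness (related to unrelated) | No | No | No, by definition |

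All three take the event out of expedited reporting. Only the third touches the primary outcome definition.

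**Step 2. Direction on relatedness.** Sites do not report events they judge unrelated (12.3.3, 12.4), so those events do not reach CI review. Every SC or USC that does reach it is already classed as related. On this attribute, disagreement over a reported event can only remove it. The one other route is the CI's power to assign relatedness where no local assessment could be obtained, which can add events.

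**Step 3. Conditions for a patient's primary outcome to change.** All must hold:

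1. The event is an SC or USC, since the review covers no others.
2. The CI reverses relatedness.
3. The reversal is carried into the outcome data, which the protocol does not state.
4. The patient has no other 30-day complication.

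The 30-day severity outcome needs only the first three. The Comprehensive Complication Index in section 13.3 sums all complications, so losing one would lower the score even if others remained.

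**Step 4. Sensitivity.** The documents give no rate of CI reversal, so this shows scale only.

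The design figure reproduces. With 45% v 30%, two-sided 5% and 90% power:

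- n = [1.960√(2 × 0.375 × 0.625) + 1.282√(0.45 × 0.55 + 0.30 × 0.70)]² / 0.15² = 217 per arm.
- Continuity correction: (n/4)[1 + √(1 + 4/(0.15n))]² = 230 per arm.
- With 10% drop-out: 230/0.9 = 256 per arm, or 512 in total, as stated in section 14.6.

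Now assume a true rate of 45% in both arms and 230 analysed per arm, so 0.45 × 230 = 103.5 patients per arm have a complication. Let a share f of these lose event status in the laparoscopic arm only. With d = 0.45f, the two-sided rejection rate (uncorrected test) is Φ((d − 1.96·se₀)/se₁) + Φ((−d − 1.96·se₀)/se₁), where se₀ is the pooled and se₁ the unpooled standard error.

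| f (assumed) | Patients changed (103.5 × f) | Rejection rate |
|---|---|---|
| 0 | 0 | 5% |
| 2% | 2.1 | 5.4% |
| 5% | 5.2 | 7.7% |
| 10% | 10.4 | 16.4% |

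Each patient counted here must meet all four conditions in Step 3, in one arm and none in the other. Suppose half of all patients with a complication had a single serious event as their only one. Then f = 5% would still need 0.05/0.5 = 10% of those patients to be re-judged unrelated, all in the same arm.

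**The case against.** The strongest case against is that the clause is a safety-reporting rule. It sits in section 12.4 and is tied to reporting to the REC. Nothing in sections 12 or 13 says a CI decision edits or deletes a case report form. By the time the CI reviews an event, the CTRU already holds the site's signed report. The statement that unrelated events are not collected governs what sites submit, not what is done with events already submitted. Other safeguards remain: annual reports to the REC, periodic reports to the TSC and DMEC, DMEC review of unblinded safety data, and the PI's own reporting of USCs to local committees. The rule permits upgrades as well as downgrades. An outright ban on downgrading would block correction of plain errors, such as marking as unexpected an event listed in Appendix 2. Which assessment feeds the analysis may also be settled in the SAP, which is not at hand.

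Most of this stands, and it limits the point. A reader might infer that trial leadership can delete confirmed events from the primary outcome, that the clause works in one direction only, or that TMG end-point validation is a power to reclassify. The documents do not support these readings. No deletion is described, the wording is symmetric, and section 20.2 lists validation under auditing.

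Two things remain. Loss of expedited reporting follows directly from the stated rule, and later periodic reports do not replace it. The link between relatedness and the endpoint is also the protocol's own definition, not an analysis detail. The CTRU check of complications in the first five patients per site (section 12) concerns accuracy of reporting and does not say whose judgement prevails.

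**Conclusion.** The point holds in two parts of unequal strength.

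**Safety reporting: established from the text.** An event the site judged serious, related and unexpected can leave expedited REC and Sponsor reporting on the judgement of one unblinded person, with no requirement to forward the site's view. It does not disappear, because the CTRU holds the report and periodic review continues.

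**Primary outcome: a possible consequence, not a stated one.** A reversal of relatedness would mean the event no longer meets the definition of a complication. Whether outcome data would follow is not stated. Changes to seriousness or expectedness cannot alter an any-grade endpoint. A patient's status would change only where the reversed event is the sole 30-day complication. The size is unknown and probably small. The sensitivity figures rest on assumed one-arm removal rates that no document supports, and they are not an estimate of bias in this trial.

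The change is worth making because it is cheap and closes an avoidable route for knowledge of allocation to affect classification.

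**What to change.** 1. **Section 12.4.** State that a CI downgrade does not stop expedited reporting. Where the CI and the site disagree, the site's assessment goes to the REC and Sponsor with the CI's view recorded alongside. The CI can still record that an event looks expected or unrelated.
2. **Section 13.1.** State that site-reported 30-day complications count in the primary and severity outcomes, and that CI reclassification is stored separately and does not alter them.
3. **Section 20.2.** State that any TMG end-point validation is done on listings without allocation.

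**Cost.** A few sentences in the protocol and a matching update to working instructions. The downside is a few more USC reports, including some the CI considers expected or unrelated. Design and sample size are unaffected.
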